7.4 Covariates

There are a number of variables with the potential to impact mother-infant outcomes and, thus, either mask or exaggerate study medication effects. Randomization will help ensure that the BUP-XR and BUP-SL groups are balanced on these variables, however, they can still be an important source of variance. Analyses will control for these variables, referred to as covariates.

Pregnancy and Addiction Services Assessment (PAASA). Study site will be included as a covariate in the secondary analyses. As noted in **section 6.4.1**, all MOMs sites will use a collaborative care model but will likely differ in the specifics of the care model used (e.g., psychosocial treatment provided etc.), which could impact mother outcomes. A review of the

literature failed to identify an instrument for characterizing models of care for the management of pregnant women with OUD. Hence, an assessment was developed for use in this protocol, the PAASA, which will be used to characterize the treatment provided by the MOMs sites. The PAASA will also be used for the health economic analysis (see **section 10.9**); the PAASA data will likely need to be supplemented with data collected through semi-structured interviews (e.g., can be collected by e-mail correspondence, phone, or in-person interviews) for this purpose. In CTN-0080, a staff member from each site will complete the PAASA at two time-points (i.e., pre-site initiation and near the end of participant data collection).

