7.4.1 Covariates for Mother Outcomes

Two covariates will be controlled for in the mother outcomes in addition to study site: 1) the use of other substances at baseline, which can impact both treatment adherence and illicit opioid use and 2) route of illicit opioid use (intravenous vs. not intravenous); the Phase 3 CAM2038 trial found that illicit use outcomes were significantly better for CAM2038, relative to BUP-SL, for participants with intravenous use.⁵⁹

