8.4 Randomization Plan

Eligible participants will be randomized in a 1:1 ratio to BUP-XR or BUP-SL. The randomization process will be performed by computer by the Data and Statistics Center (DSC). A permuted block randomization procedure with random block sizes will be implemented to balance on site, whether participants are on BUP-SL at the time of randomization (yes vs. no), and EGA at time of randomization (6 weeks - 18 weeks vs. 19 weeks - 30 weeks); EGA was used as a stratification variable in the MOTHER trial.⁴³

Table 3: Overview of Assessments and Procedures																			
Perinatal Phase:	Pregnancy					Delivery & Immediate Post-partum	Post-partum												As Needed
	Pre- Screen	Screen/ Base ¹	Random- ization ²	Week 3	Monthly Post-rand ³		Month 1	Month 2	Month 3	Month 4	Month 5	Month 6	Month 7	Month 8	Month 9	Month 10	Month 11	Month 12	
Research Visits		X	X	X	X		X		X			X			X			X*	
Screening Assessments																			
Pre-screen verbal consent	X																		
Pre-screen interview	X																		
Informed Consent		X																	
Medical record releases		X																	X
Demographics/PhenX Tier 1		X																	
DSM-5 checklist		X																	
PRISM-Suicide/Homicide		X																	
Blood Chemistry ^{4,5}		X																	
Urine Pregnancy Test		X																	
Estimated Gestational Age ^{4,5}		X																	
Treatment and Research Status		X																	
Medical and Psych History (Hx)		X																	
Drop-out Risk Assessment		X																	
Weekly Medication Check Visits ⁶																			
BUP-XR administration/documentation			Weekly administration ⁶				Weekly or Monthly administration ⁷												
BUP-SL dispense/document; adherence			Weekly - Monthly dispensing ⁸				Weekly - Monthly dispensing ⁸												
Adverse Events/Serious Adverse Events			Weekly ⁶				Weekly ⁶												
Injection Site Reaction Reporting Form																			X
Urine drug screen		X	Weekly ⁶				Weekly ⁶												
Infant sedation assessment							Weekly ⁶												
Pregnancy Test (BUP-XR)							Monthly for participants on monthly BUP-XR formulation												X
Medication Check Visit Compensation			\$20 per visit not corresponding to a research visit																
Table 3 continued on next page																			

Table 3 continued on next page

Table 3: Overview of Assessments and Procedures																			
Perinatal Phase:	Pregnancy					Delivery & Immediate Post-partum	Post-partum												As Needed

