
10.3.2 Key Outcomes

Illicit opioid abstinence during pregnancy. As noted previously, this primary outcome measure is based on urine testing. It is operationalized as the percent of expected UDSs that are negative for illicit opioids. One UDS is expected at the time of each weekly Medication Check Visit between randomization and delivery – any missing UDS is imputed as positive (see **section 10.3.5**). The number of expected UDSs will be dependent on the length of time between randomization and

delivery, thus we operationalize this primary outcome measure as the *percent* of expected UDSs that are illicit opioid-negative.

The non-inferiority design results in the following hypotheses where μ_A is the mean in arm A and Δ the non-inferiority margin:

$$H_0(BUP - XR \text{ is inferior to BUP - SL}): \mu_{XR} - \mu_{SL} \leq -\Delta$$

$$H_1(BUP - XR \text{ is non - inferior to BUP - SL}): \mu_{XR} - \mu_{SL} > -\Delta .$$

To evaluate non-inferiority at the 2.5% significance level, the two-sided 95% confidence interval for the treatment effect, $\mu_{XR} - \mu_{SL}$, will be calculated using a mixed effects model where treatment arm is a fixed effect and the three randomization factors (site, EGA and BUP-SL status at randomization) are random effects. If the lower limit of the confidence interval is greater than -0.15 (i.e., $\Delta=0.15$), we will reject the null hypothesis and conclude non-inferiority of BUP-XR to BUP-SL. Only if the null hypothesis is rejected will superiority of BUP-XR to BUP-SL be considered. This will involve examining the two-sided 95% confidence interval for the treatment effect, $\mu_{XR} - \mu_{SL}$. If the lower limit is above zero, then we can conclude that the extended-release formulation is superior to the sublingual formulation. If this order of testing is followed, then there is no need to adjust for multiplicity.^{176, 181} Additional covariates for secondary modeling are described in **section 7.4**. In the event that the distributional assumptions involved in the mixed effects model are not met, which is likely, alternative non-parametric methods will be considered for this modelling such as quantile regression.

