10.3.3 Secondary Outcomes

For binary secondary outcomes, such as the proportion of infants requiring opioid medication, and the proportion with an ICD-10 code indicating NOWS, logistic regression or Pearson's χ^2 test of association or another appropriate method will be used to assess the relationship with treatment assignment. Continuous outcomes, such as medication adherence, opioid craving during pregnancy and infant weight at delivery, will be modelled using ANOVA or an appropriate alternative (e.g., quantile regression) to evaluate the effectiveness of BUP-XR. Lastly, the number of opioid overdoses can be modeled as a count variable with possibly zero-inflation, thus a method such as Poisson or Zero-Inflated Poisson regression can be implemented.

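### Continuous secondary outcomes: section 10.3.3 names ANOVA and does not commit to the baseline score or to two of the three randomization factors, losing precision at no saving (free improvement)

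*Combined protocol and SAP*

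**What the plan says.** Section 10.3.3 (Secondary Outcomes) gives the method: "Continuous outcomes, such as medication adherence, opioid craving during pregnancy and infant weight at delivery, will be modelled using ANOVA or an appropriate alternative". The wording on method, "ANOVA or an appropriate alternative (e.g., quantile regression", names quantile regression as the only alternative, and the section names no covariate.

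Covariates come from section 7.4. Site is covered there: "Study site will be included as a covariate in the secondary analyses". Section 7.4.1 then says "Two covariates will be controlled for in the mother outcomes in addition to study site"; the two are baseline use of other substances and intravenous versus other route of opioid use. Table 2 in section 7.4.2 lists potential covariates for infant outcomes. It includes gestational age at delivery, but not the gestational-age stratum used for randomization, and not BUP-SL status.

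Section 8.4 stratifies the allocation: "A permuted block randomization procedure with random block sizes will be implemented to balance on site", BUP-SL status at randomization and gestational age at randomization (6–18 versus 19–30 weeks). In the primary model of section 10.3.2, "the three randomization factors (site, EGA and BUP-SL status at randomization) are random effects". Section 10.3.2 has postpartum abstinence follow that approach; nothing extends it to section 10.3.3.

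Table 3 schedules the Opioid Craving Scale and the SOWS-Gossop at screening/baseline, week 3, monthly in pregnancy, and postpartum months 1, 3, 6, 9 and 12.

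**The concern.** Section 10.1.2 states superiority hypotheses for adherence, craving and infant weight, among others, in a trial of about 200 women. No power is given for any of them. A pre-randomization score of the same scale is usually the best single predictor of a later score, and here it is already measured. The trial also stratified on two factors that the secondary model does not name. BUP-SL status at entry is plausibly prognostic for adherence: section 4.4.1 notes that buprenorphine dropout tends to fall in the first 30 days of treatment, and section 7.2.1.1 counts all days after dropout as non-adherent.

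The plan applies the principle elsewhere. Section 7.2.1.4 adjusts the prenatal-care index for visit attendance before randomization. Section 10.3.4.2 offers a repeated-measures mixed model for HADS, which Table 3 collects on the same schedule as craving. Craving, which carries a superiority hypothesis, is offered ANOVA.

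At stake are wider intervals and lower power for these secondary comparisons than the collected data allow.

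**Working it through.** **1. The plan's own figure.** Table 8 gives primary-outcome power. Inputs from section 10.4.2: margin 0.15, variance 0.11 (SD 0.332), one-sided 2.5%, 1:1 allocation. Power = Φ(0.15 / (0.332·√(4/N)) − 1.96).

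- N=176: 85.1% (Table 8: 84.9%)
- N=200: 89.2% (Table 8: 89.0%)

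The primary power reproduces and is not in dispute. The documents give no counterpart for continuous secondary outcomes, so the rest uses assumptions: two-sided 5%, 80% power, N=200, 1:1, no missing data.

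**2. Unadjusted detectable difference.** (1.960 + 0.842)·√(4/200) = 0.396 SD. At N=176 it is 0.422 SD.

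**3. Adding the baseline score** (craving; SOWS-Gossop if tested). ANCOVA multiplies the residual variance by 1 − ρ². The detectable difference becomes 0.396·√(1 − ρ²). Power at 0.396 SD becomes Φ(2.802/√(1 − ρ²) − 1.960). The equivalent unadjusted trial has 200/(1 − ρ²) participants.

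| Assumed ρ | Variance factor | Detectable difference, N=200 | Power at 0.396 SD | Equivalent unadjusted N | Detectable difference, N=176 |
|---|---|---|---|---|---|
| 0.3 | 0.91 | 0.378 SD | 83.6% | 220 | 0.403 SD |
| 0.5 | 0.75 | 0.343 SD | 89.9% | 267 | 0.366 SD |
| 0.7 | 0.51 | 0.283 SD | 97.5% | 392 | 0.302 SD |

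**4. Adding the gestational-age stratum and BUP-SL status** (all continuous outcomes). The variance factor is 1 − R², where R² is the share of variance that the two factors explain. Power with adjustment is Φ(2.802/√(1 − R²) − 1.960). If the strata are exactly balanced, the true SE of the unadjusted difference is √(1 − R²) times the SE that the ANOVA reports. Its actual alpha is then 2·(1 − Φ(1.960/√(1 − R²))).

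| Assumed R² | Power with adjustment | Gain over nominal 80% | Actual alpha if omitted |
|---|---|---|---|
| 2% | 80.8% | 0.8 points | 4.8% |
| 5% | 82.0% | 2.0 points | 4.4% |
| 10% | 84.0% | 4.0 points | 3.9% |
| 20% | 87.9% | 7.9 points | 2.8% |

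The gain column is a ceiling. Under the same exact balance, the unadjusted test's real power at 0.396 SD is Φ(0.842/√(1 − R²)) = 80.2%, 80.6%, 81.3% and 82.7%. The gain is then 0.5, 1.4, 2.7 and 5.3 points.

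**The case against.** The strongest reply is that the planned analysis is not a bare two-group ANOVA. Section 7.4 says that analyses will control for covariates, and it brings in site, other-substance use and route for mothers, and Table 2 for infants. That stands. The real gain is the increment beyond those terms. Baseline craving and BUP-SL status probably overlap with them and with each other, so the figures in step 3 are likely upper estimates at each assumed correlation. The sample also mixes women already on BUP-SL with women starting it, so baseline craving may predict later craving only weakly.

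A second reply is that the wording is permissive. An appropriate alternative could be ANCOVA, and section 10.3.2 says of the primary outcome "Additional covariates for secondary modeling are described in" section 7.4, so those covariates add to a model that already holds the randomization factors. Section 10.4.2 also mentions a standalone SAP. This stands in part. A reader might infer that the plan deliberately excludes the baseline score and the strata; the text does not say so. But permission is not commitment: it leaves the model open to choice after the data are seen. Section 10.4.2 cites the standalone SAP only for simulation details.

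A third reply is scope. Of the outcomes named in section 10.3.3, only craving has a baseline value. SOWS-Gossop is listed as a secondary measure in section 7.2.1.5 but has no hypothesis in section 10.1.2. This stands, so the baseline-score figures must not be carried over to adherence or birth weight.

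**Conclusion.** The point holds as a free improvement. Section 10.3.3 with section 7.4 does not commit to the same-measure baseline score or to two of the three randomization factors, although all are collected and the primary model uses all three factors.

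For craving, the detectable difference could fall from 0.396 SD to between 0.378 and 0.283 SD, for assumed correlations of 0.3 to 0.7. That is measured from an unadjusted start, so it is likely an upper range. For adherence and birth weight, the two strata are worth at most about 1 to 4 power points at an assumed R² of 2% to 10%, and up to 8 at 20%. For birth weight, the documents do not show what they would add beyond Table 2. The documents give no correlation and no R².

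Two stronger readings are tempting and unsupported. One is that the secondary comparisons are biased or have inflated error. Randomization keeps them valid, and omitting strata that predict outcome makes the test slightly conservative. The other is that every secondary interval is wider than it need be. That is true only where the omitted variable predicts the outcome beyond the covariates already planned.

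**What to change.** In section 10.3.3, replace ANOVA with ANCOVA, or with a repeated-measures mixed model across visits for craving and SOWS-Gossop. State the terms: treatment arm, site, gestational-age stratum at randomization, BUP-SL status at randomization and, where collected, the baseline value of the same measure. For adherence and birth weight, which have no baseline value, include the three randomization factors. Say that the same terms enter any alternative model, such as quantile regression, and add them to the lists in sections 7.4.1 and 7.4.2 so that the sections agree.

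The cost is a wording change before the analysis. Every variable is already collected, and no visit, assessment or participant is added.

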4.1.2 Treatment Adherence and Retention

Pregnant women with OUD face a number of challenges, including psychosocial stressors and psychiatric co-morbidity that may serve to reduce medication adherence.²⁰ In addition, because the most common concerns of BUP-maintained pregnant women are the health of their unborn infants and the potential for NAS/NOWS,²¹ expecting 100% adherence to daily self-administration of a medication that a woman worries may harm her unborn infant may be unrealistic. While the reasons are not entirely clear, treatment retention in BUP-maintained pregnant women is problematic, with retention rates estimated to be 57.7% compared to retention rates of 78.1% for methadone treatment.¹⁴ In SAMHSA's 2018 clinical guidance,¹³ it was noted that the postpartum period is a time when women are particularly vulnerable for relapse and an increased risk of overdose during the postpartum phase has been documented.²² Hence, receiving effective treatment during the postpartum period is of critical importance. The limited research on postpartum retention in opioid maintenance treatment has found dropout rates of up to 36% by 3 months postpartum and 62% by 6 months postpartum.²³ The high dropout rates are perhaps not surprising given the demands that motherhood entails, which likely serve to make daily medication adherence and treatment attendance more difficult.

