7.3.8 Opioid Overdose Tracking

Some evidence suggests that women with OUD are at heightened risk for overdose during the postpartum period.²² During the study, the participant will complete a self-report assessment about opioid overdose as outlined in **Table 3**. If a participant reports an overdose, research staff will refer her to the clinic staff who will follow up each case as specified in the site clinical SOP. A self-reported overdose resulting in naloxone rescue will be collected as an SAE.

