	Pre- Screen	Screen/ Base ¹	Random- ization ²	Week 3	Monthly Post-rand ³		Month 1	Month 2	Month 3	Month 4	Month 5	Month 6	Month 7	Month 8	Month 9	Month 10	Month 11	Month 12	
Research Visits		X	X	X	X		X		X			X			X			X*	
Sample Characteristics																			
Pregnancy Hx, HIV, Hepatitis C		X																	
Trauma History Screen		X																	
Psychosocial status		X																	
Pt. Health Questionnaire-9		X					X											X	
Thoughts about Abstinence		X																	
Timeline Followback (drug/alcohol/tobacco)		X																	
Fagerström		X																	
Opioid Overdose Risk Survey		X																	
Marijuana Use Assessment		X																	
Safety Assessments																			
Hospital Anxiety and Depression Scale		X		X	X		X		X			X			X			X	
Prior/Concomitant Meds		X		X	X		X		X			X			X			X	
Fetal Outcomes ⁴						X													
Maternal Delivery Outcomes ⁴						X													
Birth/Neonatal Outcomes ⁴						X													
Mother Efficacy Assessments																			
Opioid Craving Scale		X		X	X		X		X			X			X			X	
Adequacy of Prenatal Care Utilization ⁴						X													
Opioid Overdose Tracking				X	X		X		X			X			X			X	
SOWS-Gossop		X		X	X		X		X			X			X			X	
Other Assessments																			
PROMIS and NMOS		X			X		X		X			X			X			X	
Treatment Services Review		X			X		X		X			X			X			X	
Maternal Research Visit Compensation		\$120		\$40	\$60		\$60		\$60			\$60			\$60			\$70	
Table 3 continued on next page																			

Table 3 continued on next page

CONFIDENTIAL

Table 3: Overview of Assessments and Procedures																				
Perinatal Phase:	Pregnancy					Delivery & Immediate Post-partum	Post-partum													As Needed
	Pre- Screen	Screen/ Base ¹	Random- ization ²	Week 3	Monthly Post-rand ³		Month 1	Month 2	Month 3	Month 4	Month 5	Month 6	Month 7	Month 8	Month 9	Month 10	Month 11	Month 12		
Research Visits		X	X	X	X		X		X			X			X			X*		
Infant Assessments																				
NOWS-related and discharge outcomes ⁴						X														
ASQ-3 ⁹											X							X		
Family Psychosocial Screen ⁹											X							X		
Medical Record Releases ⁺																			X	
Infant assessment compensation											\$30							\$30		
Administrative Forms																				
Locator information form(s) ⁺	X	X			X		X		X			X			X				X	
Study Eligibility			X																	
Study Completion																		X		
Missed Visit and Visit Documentation Form		X	X	X	X		X	X	X	X	X	X	X	X	X	X	X	X		
End of Medication																			X	

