10.1.2 Secondary Hypotheses

It is also hypothesized that the BUP-XR, relative to the BUP-SL, group will have better:

1. Mother outcomes during pregnancy including significantly:
 - greater proportion of BUP adherent days during pregnancy
 - greater proportion of drug-negative urine samples
 - less opioid craving as assessed by the opioid craving scale
 - better prenatal care utilization as assessed with the APNCU index
2. Mother outcomes postpartum including significantly:
 - greater proportion of BUP adherent days
 - greater proportion of drug-negative urine samples
 - fewer opioid overdoses
 - less opioid craving as assessed by the opioid craving scale
3. Infant outcomes including significantly:
 - lower proportion of infants requiring opioid medication
 - shorter infant hospital length of stay
 - lower proportion of infants for whom adjunct medications are used to treat NOWS
 - lower proportion of infants with an ICD-10 code indicative of NOWS
 - larger head circumference
 - greater weight and length
 - greater gestational age at delivery
 - greater proportion of infants scoring above the ASQ-3 cut-off

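### The overdose count model in section 10.3.3 states no observation time, so a retention difference between arms would enter the treatment ratio

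*Combined protocol and SAP*

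**What the plan says.** Section 10.1.2 lists "fewer opioid overdoses" on BUP-XR among the postpartum mother hypotheses. For the analysis, section 10.3.3 says that "the number of opioid overdoses can be modeled as a count variable with possibly zero-inflation", and continues: "thus a method such as Poisson or Zero-Inflated Poisson regression can be implemented". It mentions no offset, rate, person-time or at-risk window.

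On ascertainment, section 7.3.8 says that "the participant will complete a self-report assessment about opioid overdose" on the Table 3 schedule. That row is marked at week 3 and monthly in pregnancy, then at postpartum months 1, 3, 6, 9 and 12. There is a second route for serious cases: "A self-reported overdose resulting in naloxone rescue will be collected as an SAE". Section 11.17.2 exempts overdoses from AE/SAE reporting unless they lead to naloxone rescue, hospitalization or death.

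Section 10.3.5 has missing-data rules for the urine outcomes and infant treatment days, and section 7.2.1.1 has one for adherence after dropout. Neither covers overdoses. Section 10.5 plans a summary of retention by arm but does not link it to the overdose model.

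**The concern.** A woman who stops attending research visits has few ways to contribute a further overdose, particularly a less serious one. In a count model without exposure time, her unobserved months are treated like months observed to be free of overdose.

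The plan gives reasons to expect retention to differ by arm. Section 4.1.2 cites "dropout rates of up to 36% by 3 months postpartum and 62% by 6 months postpartum" in opioid maintenance treatment. Section 4.4.1 notes the hypothesis that low buprenorphine levels may account for treatment dropout on BUP-SL. Section 10.1.2 predicts more adherent days on BUP-XR, and section 7.2.1.1 scores all days after study dropout as non-adherent.

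At stake is a stated postpartum hypothesis with clear safety relevance. An arm that keeps more women under observation could lose credit for a lower overdose rate, or appear worse, because it observed more time.

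**Working it through.** **The plan's own figures.** None is given for overdoses. The only power figures are for the primary outcome (Table 8: 84.9% at N=176, 89.0% at N=200). With margin 0.15, variance 0.11 and two-sided 5%, a normal approximation gives 85.1% and 89.2%, so they reproduce. This point does not touch them.

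**Formula.** Let r be the overdose rate and T the mean observed time in each arm, with the rate unrelated to leaving. Then

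ratio of mean counts = (r_XR × T_XR) / (r_SL × T_SL) = true rate ratio × (T_XR / T_SL).

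Mean observed time is the area under the retention curve over 12 postpartum months.

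**Inputs.** From the documents: about 200 women, 1:1, so 100 per arm; 12 months postpartum; the 36% and 62% of section 4.1.2. Assumed, because the documents do not give them: study dropout in each arm, and overdose rates of 0.1, 0.2 and 0.5 per woman-year.

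**Milder study dropout** (assumed 25% by 6 months on BUP-SL at constant hazard, none later). The hazard is −ln(0.75)/6 = 0.0479 per month.
- BUP-SL: 0.25/0.0479 + 6 × 0.75 = 9.71 months.
- BUP-XR, three quarters of that hazard (6-month retention 0.75^0.75 = 0.806): 10.23 months; ratio 1.05.
- BUP-XR, half that hazard (6-month retention 0.866): 10.78 months; ratio 1.11.

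**Study dropout equal to the cited treatment dropout** (linear between time points, flat after 6 months).
- BUP-SL: 3 × (1 + 0.64)/2 + 3 × (0.64 + 0.38)/2 + 6 × 0.38 = 6.27 months.
- BUP-XR, a quarter less dropout (27%, 46.5%): 2.595 + 1.898 + 3.21 = 7.70 months; ratio 1.23.
- BUP-XR, half the dropout (18%, 31%): 2.73 + 2.265 + 4.14 = 9.14 months; ratio 1.46.

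A piecewise-exponential curve through the same two points gives 1.19 and 1.44 at three quarters and half the hazard (1.17 and 1.37 with no dropout after 6 months).

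**As counts.** At 0.2 per woman-year in both arms, the last scenario expects 100 × 0.2 × 6.27/12 = 10.5 overdoses on BUP-SL and 100 × 0.2 × 9.14/12 = 15.2 on BUP-XR.

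**Effect on a true ratio of 0.70.** It would show as 0.70 × 1.05 = 0.74, 0.70 × 1.11 = 0.78, 0.70 × 1.23 = 0.86 or 0.70 × 1.46 = 1.02.

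**Simulated type I error** (Poisson regression, 100 per arm, equal true rates, two-sided 5%):

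| Scenario | Without offset | With offset |
|---|---|---|
| 25% dropout, a quarter less on BUP-XR | 4–6% over the three rates | – |
| 25% dropout, half the hazard on BUP-XR | 4%, 6%, 8% at 0.1, 0.2, 0.5 | – |
| Cited dropout continuing to 12 months, half the hazard on BUP-XR | 5%, 13%, 27% at 0.1, 0.2, 0.5 | 2%, 4%, 4% |
| Cited dropout flat after 6 months, half on BUP-XR | 14.9%, 32.3% at 0.2, 0.5 | 3.5%, 5.1% |

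**What the offset does not repair.** If overdose risk and dropout share a gamma frailty of variance 1 (cited dropout, half the hazard on BUP-XR, no treatment effect), the ratio with the offset is still about 1.2, and type I error is about 12% at 0.5 per woman-year.

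**The case against.** The wording is permissive. It offers a possible model and an example of a method, and an offset is routine in either one. A reader might infer that the plan has decided to ignore follow-up time; the text does not say so. Section 10.4.2 mentions a standalone Statistical Analysis Plan, though only for the simulation details. This part stands: the defect is an unspecified observation time.

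The cited dropout is an upper figure for leaving treatment, whereas the bias depends on leaving study visits. The protocol separates the two. Women who stop medication are encouraged to keep attending (sections 8.7.1 and 9.5), those who switch to methadone or naltrexone may stay in the study (9.7), missed visits are actively tracked (7.7) and visits are paid (8.6). No document gives a BUP-XR dropout figure, so any reduction is assumed. This also stands and removes 1.46 as an expected value.

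A woman who leaves does not necessarily contribute zero. Overdoses with naloxone rescue, hospitalization or death are reportable, and dropouts' records remain accessible (8.1), although overdose is not listed for abstraction. The form's recall period is not given, so a missed visit may be made up at the next one. These points reduce the loss but do not remove it.

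Finally, if BUP-XR retains better, the error runs against BUP-XR and cannot create the hypothesized benefit. That is true in that scenario, but a masked benefit or a spurious excess of overdoses would still mislead.

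**Conclusion.** The point holds as a cheap improvement. Followed as written, section 10.3.3 compares counts that mix the overdose rate with the time over which overdoses could be reported, and nothing else in the plan deals with the unobserved time.

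The distortion equals the ratio of observed times: about 1.05 to 1.1 under moderate study dropout and about 1.2 to 1.5 if study dropout were as high as the cited treatment dropout. Type I error lies between nominal and about 30%, and stays near 5% when overdoses are rare or study dropout is moderate. All of this rests on assumed dropout and event rates, and on the rate being unrelated to leaving.

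Two stronger readings are not supported. One is that BUP-XR will appear to have more overdoses: the direction depends on which arm is observed longer and on the true rates, and a real reduction may be shrunk without being reversed. The other is that zero-inflation must be dropped: it does not itself adjust for partial follow-up, but a zero-inflated model can carry an offset. The primary outcome, the key secondary outcomes and the sample size are unaffected.

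**What to change.** In section 10.3.3, specify the postpartum overdose model as Poisson, negative binomial or zero-inflated Poisson with an offset of log(observed time), running from the start of the postpartum phase to the last completed overdose assessment. Report events, person-time and the rate ratio with its 95% CI, with events and person-time shown by arm. Count in this model only overdoses inside that window, and list separately any later ones known from SAE reports or records, so that numerator and denominator match.

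Add a sensitivity analysis for informative dropout, for example assigning a higher overdose rate to unobserved time and varying it by arm.

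The cost is SAP wording; visit dates are already recorded. The downside is that the offset assumes the rate after dropout equals the observed rate, which is why the sensitivity analysis is needed. Women with no postpartum overdose assessment add no person-time, and their number by arm should be reported.
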